10.7 APPENDIX 12: PROTOCOL AMENDMENT HISTORY

Not applicable.

## VERSION HISTORY

This Statistical Analysis Plan (SAP) for study LTS17352 is based on the protocol dated 30-Jun-2021. This section summarizes major changes to the statistical analysis features in the SAP. The first participant was enrolled on 30-Oct-2021.

**Table 1 - Major changes in statistical analysis plan**

SAP Version	Approval Date	Changes	Rationale
1.0	07-Oct-2022	Not Applicable	Original version

## 1 INTRODUCTION

### 1.1 STUDY DESIGN

This is a multi-center, single treatment-group, open-label study with repeated dose design.

### 1.2 INTERVENTION GROUP

Sutimlimab dose is 6.5 g for participants whose weight is  $\geq 39$  kg to  $< 75$  kg or 7.5 g for participants  $\geq 75$  kg at baseline.

### 1.3 OBJECTIVE AND ENDPOINTS

**Table 2 - Objectives and endpoints**

	Objectives	Endpoints
Primary	

Evaluation of overall safety profile for sutimlimab

	

Adverse event (AE) /serious adverse event (SAE) / Adverse event of special interest (AESI)

Secondary	

Not applicable

	

Not applicable

## 2 SAMPLE SIZE DETERMINATION

Up to 7 participants will be enrolled to this study.

Up to 7 participants are expected to complete CARDINAL study or CADENZA study, and to be enrolled to this study.

## 3 ANALYSIS POPULATIONS

The following population for analyses is defined:

**Table 3- Populations for analyses**

Population	Description
Safety	All enrolled participants who take at least 1 dose of study intervention.

## 4 STATISTICAL ANALYSES

### 4.1 GENERAL CONSIDERATIONS

Continuous data will be summarized using the number of observations available, mean, standard deviation (SD), median, minimum, and maximum. Categorical and ordinal data will be summarized using the count and percentage of participants.

Baseline is defined as the day of the first dose (Day 0).

Unless otherwise specified, analyses will be performed by intervention group and overall for baseline and demographics characteristics.

Among the descriptive statistics, the mean, standard deviation, and median should be rounded to one more digit than the number of digits in the measurement data, and the minimum and maximum values should have the same number of digits as in the measurement data. Percentages should be expressed to the first decimal place.

### 4.2 BASELINE AND DEMOGRAPHICS CHARACTERISTICS

Descriptive statistics will be calculated for age (year), height (cm), weight (kg), BMI (kg/m^2) and Presence of CAD circulatory symptoms at baseline by intervention group and overall.

### 4.3 PRIMARY ENDPOINT(S) ANALYSIS

#### 4.3.1 General common rules for primary endpoint(s) analysis

The primary analyses will be performed on the safety population as defined in [Section 3](#).

TEAEs are defined as AEs that developed, worsened or became serious during the treatment-emergent period.

The primary focus of AE reporting will be on TEAEs.

An AE with incomplete or missing date/time of onset (occurrence, worsening, or becoming serious) will be classified as a TEAE unless there is definitive information to determine it is a pre-treatment or a post-treatment AE.

Multiple occurrences of the same event in the same participant will be counted only once in the tables.

The AE tables will be sorted as indicated in [Table 4](#).

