9.3.3.1 Adverse events

General common rules for adverse events

The primary focus of adverse event reporting will be on treatment-emergent adverse events (TEAEs). Ongoing AE from CARDINAL study and CADENZA study will be recorded in medical history. New AE that started between end of CARDINAL/CADENZA and start of this study will be recorded in medical history.

TEAEs are defined as AEs that developed, worsened or became serious during the treatmentemergent period (from the time from the first dose of study treatment in this study to the last contact on study).

Analysis of all adverse events

Summary table will be provided for the following types of TEAEs: all TEAEs, all treatment emergent AESI (defined with a PT or a prespecified grouping), all treatment emergent SAEs and all TEAEs leading to permanent treatment discontinuation.

The AE summaries will be generated with number (%) of participants experiencing at least one event.

All deaths will be listed.

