#### 4.3.2 Adverse event

##### Analysis of all adverse events

The overview of TEAE with the details below will be generated:

- Total number of TEAEs
- Number of subjects with at least one TEAE
- Number of subjects with at least one related TEAE
- Total number of treatment emergent AESIs
- Number of subjects with at least one treatment emergent AESI
- Number of subjects with at least one related treatment emergent AESI
- Total number of treatment emergent SAEs
- Number of subjects with at least one treatment emergent SAE
- Number of subjects with at least one related treatment emergent SAE
- Number of subjects who discontinued treatment and/or the study due to a TEAE
- Number of deaths

The AE summaries of Table 5 will be generated with number (%) of participants experiencing at least one event (if these types of AE are observed).

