**Table 5 - Analyses of adverse events**

Type of AE	MedDRA levels
TEAEs	Primary SOC and PT
Treatment emergent AESIs	Primary SOC and PT
Treatment emergent SAEs	Primary SOC and PT
TEAEs leading to permanent treatment discontinuation	Primary SOC and PT
Deaths	Primary SOC and PT

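### Does the once-only adverse event counting rule in SAP 4.3.1 undercut the event totals that SAP 4.3.2 asks for?

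*SAP*

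**What the plan says.** SAP 4.3.1, among the common rules for the primary endpoint, states: "Multiple occurrences of the same event in the same participant will be counted only once in the tables". The next sentence sends the reader to Table 4 for the sort order of the adverse event tables. Table 4 has a single presentation, by SOC and PT.

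SAP 4.3.2 then orders two kinds of output.

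- **An overview.** It contains "Total number of TEAEs", the corresponding total for adverse events of special interest (AESIs), and "Total number of treatment emergent SAEs". Each total is followed by its own row for participants with one or more such events.
- **The Table 5 summaries.** Every type of event is shown at the level "Primary SOC and PT", as number and percentage of participants.

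The participant format agrees with SAP 4.1 ("Categorical and ordinal data will be summarized using the count and percentage of participants") and with Protocol 9.3.3.1 ("The AE summaries will be generated with number (%) of participants experiencing at least one event"). Protocol 9.3.3.1 sets the treatment-emergent period as running "from the first dose of study treatment in this study to the last contact on study". SAP 4.4.1 summarises treatment duration, and SAP 4.6 plans listings of adverse events, infusions, visit dates and completion or discontinuation.

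**The concern.** The rule covers the tables without exception, and the overview is a table. If it governs the overview, the three event totals stop being event totals. Each becomes a count of distinct participant-by-event combinations, and the rule does not say whether two events are the same at SOC or at PT level. Adverse events are the only endpoint and dosing is repeated, so recurrence in one participant is plausible. Two programmers could then report different totals from the same data.

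A second worry concerns time. Treatment is open-ended. Under footnote h of the Schedule of Activities, follow-up after a switch to the marketed drug can be as short as about 2 weeks instead of 9. The Table 5 percentages carry no participant-time, and repeats by PT would be visible only in the listings. Event counts by PT and a rate per participant-year look like cheap remedies.

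**Working it through.** **1. The plan's own figure.** SAP 4.4.1 gives 20 protocol-specified doses for treatment completed at Day 259. Doses fall on Days 0 and 7, then every 14 days from Day 21: 2 + (259 − 21)/14 + 1 = 2 + 17 + 1 = 20. The figure is reproduced.

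**2. What the literal rule would do.** Take invented data: participant 1 has event A three times and event B once, participant 2 has A twice, and participant 3 has C once.

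| Row | Every occurrence counted | Once-only rule applied literally |
|---|---|---|
| Total events | 3 + 1 + 2 + 1 = 7 | 2 + 1 + 1 = 4 |
| Participants with at least one event | 3 | 3 |

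The total loses (7 − 4)/7 = 43%. For a single term occurring k times in one participant the loss is 1 − 1/k: 50% for k = 2, 80% for k = 5, and 95% for k = 20 (once at every infusion in the Day 259 example). These values of k are assumptions, and each loss is for that one term. The loss in the whole row depends on all the other events. The participant row never changes.

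**3. Which reading the text supports.**

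- The rule is followed at once by the sort order for tables by SOC and PT, so those are the tables under discussion.
- Those tables count participants, for whom counting once at each displayed level is correct. Table 5 supplies the levels.
- SAP 4.3.2 names the overview separately from the Table 5 summaries.
- In the overview, the event total and the participant count are separate rows. A total of participant-by-event combinations would be neither events nor participants.
- For AESIs, Table 6 lists only symptomatic overdose and pregnancy, so repeats in that row are unlikely.

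**4. Participant-time.** Take a first dose on Day 0 and a last dose on Day 259.

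- Treatment duration under SAP 4.4.1: 259 − 0 + 15 = 274 days, and 274/7 = 39.14 weeks.
- First dose to end of follow-up: 259 + 14 + 1 = 274 days with a 2-week tail, or 259 + 63 + 1 = 323 days with 9 weeks. The ratio 323/274 is 1.18, so 18% longer.
- If all 7 participants had this duration (an assumption): 7 × 274/365.25 = 5.25 participant-years, or 7 × 323/365.25 = 6.19.

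Unequal treatment length matters more than the tail. The documents give no entry dates after the first, so assume a common calendar end, a 2-week tail, and entry 0, 12 or 26 weeks after the first participant. Observation is then 274, 274 − 84 = 190, or 274 − 182 = 92 days. With hazard h per year, P(at least one event) = 1 − exp(−h × days/365.25):

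| h (assumed) | 274 days | 190 days | 92 days |
|---|---|---|---|
| 0.5 | 31.3% | 22.9% | 11.8% |
| 1 | 52.8% | 40.6% | 22.3% |
| 2 | 77.7% | 64.7% | 39.6% |

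**5. What a rate would add.** Use the exact Poisson 95% interval over 5.25 participant-years.

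- 5 events: 5/5.25 = 0.95 per year, interval 0.31 to 2.22. The upper limit is about seven times the lower.
- 20 events: 20/5.25 = 3.81 per year, interval 2.33 to 5.88.

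**The case for a change.** The strongest argument for a change is that Table 5 already counts participants with at least one event, so the once-only rule alters nothing there. The only outputs it can alter are the event totals. On that view a programmer who takes every SAP sentence to have an effect would apply it exactly where it does harm, and one clarifying clause would prevent this.

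Part of this stands. The sentence is unqualified, and in Table 5 it repeats what the format already implies. But saying that a participant counts once per term is an ordinary reminder in adverse event rules, and its redundancy does not show that it was aimed at the overview. The specific rows in SAP 4.3.2, paired as events and participants, settle the matter against the general sentence. If a programmer did collapse repeats, the adverse event listing for at most 7 participants would expose the error on a simple recount.

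On time at risk, it is true that percentages depend on follow-up, as the assumed figures show. But there is no comparator for unequal follow-up to bias. The reader has the treatment duration summary, whose mean multiplied by the number of participants gives total treatment time, and the infusion, visit-date and completion listings give the individual course. Events by PT and rates are therefore a matter of preference. A rate also brings its own difficulty. Protocol 7.1.1 allows follow-up beyond 9 weeks until an event recovers or stabilises. A rate limited to scheduled adverse event collection could therefore have a numerator that differs from the overview total, which uses the protocol's period to last contact.

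**Conclusion.** The concern rests on a loosely worded sentence whose meaning the surrounding text supplies: once per participant at each SOC and PT level in the Table 5 summaries, and every occurrence in the overview totals. An analyst would follow this without instruction. Only the three totals could be affected, and only if the sentence were applied against its context and events recurred. Participant counts and percentages are the same either way. The 43% loss comes from invented data, and the 50%, 80% and 95% losses from assumed recurrence.

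The overview already plans event totals, so only counts by SOC and PT are absent, and the participant format follows the protocol. Participant-time and rates would change no conclusion in a single-group descriptive study of this size, where even the assumed 5.25 participant-years leaves an interval of 0.31 to 2.22 per year for 5 events. The entry delays and hazards used above have no source in the documents and serve only to show the range. No change to the plan is needed.

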**Table 4 - Sorting of AE tables**

AE presentation	Sorting rules
SOC and PT	By the internationally agreed SOC a order and decreasing frequency of PTs b,c

a Appendix2 for sort order of SOC  
b Sorting will be based on the overall incidence.  
c The table of all TEAEs presented by SOC and PT will define the presentation order for all other tables (eg, treatment-emergent SAE) presented by SOC and PT, unless otherwise specified.

#### 4.3.2 Adverse event

##### Analysis of all adverse events

The overview of TEAE with the details below will be generated:

- Total number of TEAEs
- Number of subjects with at least one TEAE
- Number of subjects with at least one related TEAE
- Total number of treatment emergent AESIs
- Number of subjects with at least one treatment emergent AESI
- Number of subjects with at least one related treatment emergent AESI
- Total number of treatment emergent SAEs
- Number of subjects with at least one treatment emergent SAE
- Number of subjects with at least one related treatment emergent SAE
- Number of subjects who discontinued treatment and/or the study due to a TEAE
- Number of deaths

The AE summaries of Table 5 will be generated with number (%) of participants experiencing at least one event (if these types of AE are observed).

**Table 5 - Analyses of adverse events**

Type of AE	MedDRA levels
TEAEs	Primary SOC and PT
Treatment emergent AESIs	Primary SOC and PT
Treatment emergent SAEs	Primary SOC and PT
TEAEs leading to permanent treatment discontinuation	Primary SOC and PT
Deaths	Primary SOC and PT

##### Analysis of adverse events of special interest (AESIs)

Adverse events of special interest (AESIs) will be selected for analyses as indicated in Table 6. Number (%) of participants experiencing at least one event will be provided for each event of interest. Tables will be sorted as indicated in Table 4.

**Table 6 - Selections for AESIs**

AESIs
Symptomatic overdose with study drug
Pregnancy

## **4.4 OTHER ANALYSES**

### **4.4.1 Extent of exposure**

Study drug exposure, measured by the duration of study treatment and total actual BIVV009 dose, will be summarized for the Safety population. For these items, the mean, standard deviation, and median will be displayed to the second decimal place, and the minimum and maximum values will be displayed to the first decimal place.

The duration of the study treatment (in weeks) is defined as (date of last dose – date of first dose + 15)/7.

The actual dose administered at each infusion is calculated as (Total volume administered / Total volume prepared) \* assigned dose.

The total BIVV009 dose is the summation of all actual dose administered.

Study drug compliance will also be summarized for Safety population.

Study drug compliance for a subject is measured by the percent of number of doses received out of the number of protocol specified doses. For example, for a subject who completes the study treatment at Day259, the number of protocol specified doses is 20. The compliance of the subject will be the number of doses received divided by 20 expressed in percentage. For a subject who discontinues early, the number of protocol specified doses is the number of scheduled doses prior to the date of discontinuation.

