- f Sutimlimab doses of 6.5 g (if ≥39 kg to <75 kg) or 7.5 g (if ≥75 kg) based on participant's baseline body weight will be administered via IV infusion over ~60±5 minutes on Days 0, 7, and every other week thereafter during treatment period. Participants with underlying cardiopulmonary disease may receive a 2-hour infusion with Sponsor approval. If a participant misses a scheduled dose (outside of the 2-day window or >17 days since last dose), they must return to site (unscheduled visit) to receive another loading dose and then resume bi-weekly dosing schedule one week later.
- g Adverse events will be recorded from the time the participant provides signed informed consent through the safety follow-up period.
- h If participants switch to marketed drug, safety follow-up should be continued until the day of infusion of marketed drug or for 9 weeks, whichever comes first. In some cases, if the transition to marketed drug may occur without interruption in the every other week infusion schedule, this time period could be approximately 2 weeks.

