4.3 JUSTIFICATION FOR DOSE

The same dose as used in CARDINAL and CADENZA studies was chosen. CARDINAL study has already confirmed safety and efficacy at below (1).

6.5 g for participants whose weight at baseline is \ge 39 kg to <75 kg or 7.5 g for participants \ge 75 kg at baseline.

The dosing schedule consists of an initial dose (Day 0), followed by a dose one week later (Day 7), which is followed by a maintenance dose every other week beginning on Day 21.

Participants who miss a dose (ie, outside the dosing window or >17 days since last dose) should return to the study site for an unscheduled visit 1 as soon as possible in order to receive an additional loading dose and then resume bi-weekly dosing schedule 1 week after the loading dose.

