7.1.2 Temporary discontinuation

Temporary intervention discontinuation may be considered by the Investigator because of suspected AEs or disruption of the clinical trial due to a regional or national emergency declared by a governmental agency. For all temporary intervention discontinuations, duration should be recorded by the Investigator in the appropriate pages of the CRF.

Temporary intervention discontinuation decided by the Investigator corresponds to more than 1 dose not administered to the participant.

In case of temporary discontinuation with dosing gap >17 days since last dose, participants must return to site (unscheduled visit) to receive another loading dose and then resume bi-weekly dosing schedule 1 week after the loading dose.

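### SAP 4.4.1 counts doses received and doses due by rules that do not match: compliance exceeds 100% if a dose is given on the discontinuation date, and re-loading infusions have no counting rule

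*SAP*

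**What the plan says.** SAP 4.4.1 (Extent of exposure) defines compliance as follows: "Study drug compliance for a subject is measured by the percent of number of doses received out of the number of protocol specified doses". It gives a worked example: "for a subject who completes the study treatment at Day259, the number of protocol specified doses is 20", and then "The compliance of the subject will be the number of doses received divided by 20 expressed in percentage". For early stopping the rule is different: "For a subject who discontinues early, the number of protocol specified doses is the number of scheduled doses prior to the date of discontinuation". The SAP sets no date limit on doses received. It does not define the discontinuation date or tie it to the last infusion. Protocol 7.1.1 asks only that a permanent discontinuation be entered in the CRF once it is regarded as confirmed.

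The regular schedule is Day 0, Day 7, Day 21 and every two weeks after that (Protocol 1.1, 4.3 and Table 2), with a window of ±2 days on the two-weekly visits (Protocol 1.3).

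The protocol also has a second dosing path. Footnote f of the Schedule of Activities begins "If a participant misses a scheduled dose (outside of the 2-day window or >17 days since last dose" and continues "they must return to site (unscheduled visit) to receive another loading dose and then resume bi-weekly dosing schedule one week later". Protocol 4.3 repeats this for a missed dose: the participant returns "in order to receive an additional loading dose and then resume bi-weekly dosing schedule 1 week after the loading dose". Protocol 7.1.2 applies the same path after an interruption: "In case of temporary discontinuation with dosing gap >17 days since last dose". SAP 4.4.1 does not mention re-loading infusions.

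**The concern.** A compliance percentage is meaningful only if its numerator and denominator cover the same period and the same kinds of infusion. Here they may differ in two ways.

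- **Cut-off.** The completer's denominator includes the last day and the early discontinuer's does not. An infusion given on the discontinuation date is then received but never due, and the ratio passes 100%.
- **Re-loads.** A re-loading infusion is given at an unscheduled visit, yet the protocol requires it. The SAP does not say whether it is a dose received, a protocol specified dose, or both. Two programmers could derive different values from one infusion record, and one of those values can hide a missed dose.

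At stake is the accuracy of one descriptive table. With at most 7 participants, a single odd value would show in the mean and the maximum.

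**Working it through.** **Inputs.** Schedule: Days 0, 7, 21, then every 14 days (Protocol 4.3). Re-load path: one infusion g days after the last dose, the next 7 days later, then every 14 days (Protocol 1.3 footnote f). Compliance rules and the figure of 20: SAP 4.4.1.

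**1. The SAP's own figure.** Doses through Day 259 = 2 (Days 0 and 7) + (259 − 21)/14 + 1 = 2 + 17 + 1 = 20. This agrees with the SAP. Counting only doses before Day 259 gives 19, so the example includes the last day.

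**2. Discontinuation on an infusion day.** If k scheduled doses have been given up to and including that day, the SAP rule gives k/(k − 1).

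| Discontinuation date, dose given that day | Received | Scheduled before that date | Compliance |
|---|---|---|---|
| Day 0 | 1 | 0 | undefined |
| Day 7 | 2 | 1 | 200% |
| Day 35 | 4 | 3 | 133.3% |
| Day 133 | 11 | 10 | 110% |
| Day 259 | 20 | 19 | 105.3% |

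If the participant stops on Day 133 before that day's infusion, the value is 10/10 = 100%. If the date is recorded after the infusion day and before the next scheduled dose, it is 11/11 = 100%. For scale, assume the other six participants are at 100%: one value of 110% makes the mean (6 × 100 + 110)/7 = 101.4%.

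**3. One missed dose with a re-load, Day 259 end.** Let L be the day of the last dose before the gap. The regular doses at L+14, L+28, L+42 and so on are replaced by doses at L+g, L+g+7, L+g+21 and so on. The second replacement dose falls on or before L+28 when g + 7 ≤ 28, that is, when g ≤ 21. In that case the total by Day 259 is fully restored.

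| Gap g | Received | Missed | Re-load in numerator only, divisor 20 | Re-load in both terms, miss kept: received/(received + missed) |
|---|---|---|---|---|
| 17–21 days | 20 (19 regular + 1 re-load) | 1 | 20/20 = 100% | 20/21 = 95.2% |
| 22–28 days | 19 (18 regular + 1 re-load) | 1 | 19/20 = 95.0% | 19/20 = 95.0% |

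The 100% result holds for a last dose before the gap from Day 7 to Day 231. After Day 0 or Day 245, a gap of 17 to 21 days gives 19/20 = 95.0%. The 17-day gap is a miss only through the window limb of footnote f, when the preceding dose was on schedule. The limb of more than 17 days starts at 18.

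**4. Dependence on the end date.** Suppose the calendar count instead stops at the participant's own last, shifted infusion, with a last dose on Day 105 before the gap. Gaps of 17 to 20 days then end on Days 255 to 258 and give 20/19 = 105.3%. A 21-day gap gives 20/20 = 100%, and gaps of 22 to 28 days give 19/19 = 100%. The range of 17 to 21 days therefore belongs to the Day 259 end and is not a general property.

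**The case against.** Several points on the other side have force.

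- **The re-load is itself specified by the protocol.** On that reading it belongs in the denominator, the value is 20/21 = 95.2%, and nothing is misstated. The figure of 20 can be seen as illustrating an undisturbed course. This reading is fair, so the 100% value is one possible outcome and not the necessary one. What stands is that the SAP does not choose.
- **Compliance here is a count and does not measure timing.** Twenty infusions by Day 259 could reasonably be called 100%. That is a choice of what to measure. However, footnote f treats the same event as a missed scheduled dose, and a table showing 100% would not reveal it.
- **The cut-off case needs several conditions together.** The participant must discontinue early, the discontinuation date must equal an infusion date, and that infusion must have been given. The documents do not show how the CRF dates the event, so its frequency is unknown. The rule as written still allows the result.
- **A programmer might cut the numerator at the same point.** That would give 10/10 at Day 133, but the SAP does not say so, and a dose that was given would be dropped.

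A reader might go further and infer that re-loading generally hides missed doses. The documents do not support that: at a Day 259 end, gaps of 22 to 28 days still score 95.0%. A reader might also treat every gap of 29 to 35 days as two missed doses. An infusion 29 or 30 days after an on-schedule dose lies within ±2 days of the second due day (L+28), so by the window only one dose was missed. No figures are given here for those longer gaps.

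**Conclusion.** The point holds in a limited form. The firmer part is the cut-off. SAP 4.4.1 includes the last day for completers and excludes it for early discontinuers, with no matching limit on doses received. A dose on the discontinuation date then gives an impossible value: 110% at Day 133, more for earlier dates. This assumes that the date coincides with an infusion and that the exclusion is read strictly.

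The secondary part is an ambiguity. With a Day 259 end and a last dose from Day 7 to Day 231 before the gap, one miss re-loaded at 17 to 21 days is 100% or 95.2% depending on the reading.

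The impact is minor and the change is optional. Compliance is a descriptive item under SAP 4.4, is not an endpoint, defines no analysis population and covers at most 7 participants. The infusion listing in SAP 4.6 will show each gap. A reader might infer that the safety conclusions are affected, but nothing in the documents links compliance to the adverse event analysis.

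**What to change.** Amend SAP 4.4.1 as follows.

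1. **Cut-off.** For early discontinuers, the denominator is the scheduled doses before the discontinuation date, plus the dose on that date if it was given. Count doses received to the same cut-off. Day 133 with the dose given becomes 11/11 = 100%. A participant who stops that day before the infusion stays at 10/10, as under the current rule, and is not charged a miss.
2. **Re-loads.** Count each re-loading infusion in both numerator and denominator. Keep each missed scheduled dose in the denominator, and count later doses on the shifted schedule. In the Day 259 cases of step 3 with a last dose from Day 7 to Day 231, one miss then gives 95.2% for a gap of 17 to 21 days and 95.0% for 22 to 28 days. A missed dose always lowers the figure, whichever end date applies.
3. **Reporting.** Give the number of missed and re-loading infusions per participant beside the percentage.

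The cost is two or three sentences and two derived counts. The infusion dates are already recorded (Protocol 6.4) and listed (SAP 4.6), so no new data are needed. The change concerns counting only and leaves every dosing rule as it is.
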